Note. Some of the materials included as appendices with this submission will be further refined by the study team. Upon completion, final versions will be submitted for IRB review and approval in a future amendment. IRB approval will be obtained prior to the use of the final versions in the study.

Figure 1. Project Overview

Health Systems and Clinics

The P01 program will involve a total of 10 health systems in four states. A letter of support from each system has been included. Several of the health systems include multiple clinics. Similar to the other projects in this P01 program, all activities and participants will stem from these health systems/clinics (as described below).

Year 1 Preliminary Activities

During Year 1, we will conduct two necessary preliminary activities outside of the GRT portion of the study: training of patient navigators and provider education sessions.

Training of Patient Navigators

PN will be provided during the randomized trial to help women both: a) use/return their HPV self-test (if they do not initially return their device); and b) attend an in-clinic follow-up visit if their returned self-test is positive for high-risk HPV infection. Patient navigators (PNs) will perform the following activities during the trial: a) provide information about HPV, cervical cancer, and screening; b) address patients' concerns/barriers about HPV self-testing and attending a follow-up visit (if needed); c) help set goals and plans for achieving these outcomes; and d) provide social support. These activities are key components of behavior change technique³³ and were used in our past PN work.³⁴ The PNs will be health system/clinic staff that have agreed to serve as PNs for this project.

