We will next mail all identified potentially eligible women a standard reminder letter to get a clinic-based cervical cancer screening test (e.g., Pap test) (see Appendix). The letter will indicate that, according to EHR, they are due for a clinic-based cervical cancer screening test and encourage them to contact their clinic to schedule a test (contact information for the clinic will be provided). All letters will appear on clinic/health system letterhead and be signed by a clinic representative. Many health systems have utilized this type of reminder letter for cervical cancer screening,³⁶ so it can be considered "usual care." We think it is important that all potentially eligible women receive this letter that encourages clinic-based cervical cancer screening test before any HPV self-tests are sent. The clinics will mail all of the reminder letters to women. Members of the project team will not have access to any identifying information (including contact information) of the patients. All communication between the project team and clinics about patients will involve only ID numbers.

We will allow about 4-5 months for women who are sent a reminder letter to receive a clinic-based cervical cancer screening test. At the end of the this time period, we will work with the clinics/health systems and use EHR to

identify women who received a clinic-based cervical cancer screening test since the reminder letters were sent. Any woman who has received a test will not continue in the project, as they are no longer unscreened/underscreened. Based on the mean effect size of past studies of mailed cervical cancer screening reminder letters, we anticipate that only about 5% of women who are sent a reminder letter will receive a clinic-based test during the 4-5 month period.³⁶

Randomization

Health systems will be randomized to one of two treatment groups (Group 1 or Group 2) for the cervical cancer prevention program (Figure 1). A 1:1 allocation scheme stratified by state will be used (i.e., five systems per treatment group). Health system will be the unit of randomization. All clinics in a health system will be in the same treatment group.

Year 2 Randomized Trial Activities

[figure not shown]
Group 1: Early Intervention

Group 1 clinics/health systems will receive Early Intervention during Year 1, including HPV self-test devices sent to women (patient-level component) and PN (system-level component). Figure 2 provides an overview of these components.

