Group 1 clinics/health systems will continue with the Sustainability phase, as described above during Year 5. Group 2 clinics/health systems will also enter the Sustainability phase, as described above, during Year 5. In this phase, 100 women across Group 1 health systems and 100 women across Group 2 health systems who remain unscreened/underscreened will be randomly sampled from the sampling frame and sent an HPV self-test.

Data Collection for Year 5

Data collection activities (Medical Record Review and Patient Satisfaction Survey) will be identical to those described for Year 3.

Statistical Methods: Analyses and Evaluation

We will conduct analyses/evaluation of each outcome type recommended for implementation research:³² implementation, service, and client outcomes.

Aim 1 (Service Outcomes)

Service outcomes will include intervention effectiveness, equitableness, and safety (Table 1). We hypothesize the intervention will increase cervical cancer screening and that PN will increase HPV self-test return among women who do not initially return their self-test (Hypothesis 1a). We think PN will increase HPV self-test return among these initial non-returners given PN's positive effect on health outcomes in past studies.²⁶⁻²⁹ Lastly, we hypothesize the increase in screening will be similar across patient characteristics (i.e., equitableness)(Hypothesis 1b).

Table 1. Service Outcomes and Data Sources

Outcome	Measure	Level	Data Source
Effectiveness	Cervical cancer screening	Patient-level	HPV self-test data and medical records
Equitableness	Demographic and health-related characteristics	Patient-level	Medical records
Safety	Reported issues in using an HPV self-test	Patient-level	Patient satisfaction surveys

Measures

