The patient-level effectiveness outcome and primary outcome for our project will be whether or not women get "screened" during the project. There are three ways a woman can be considered "screened." The first is to return their HPV self-test and test negative for high-risk HPV types. The second is to return their HPV self-test, test positive for high-risk HPV types, and then attend a follow-up appointment at their health system. We are requiring these women to attend a follow-up appointment to be considered "screened" given their HPV infection. The third way is to receive a clinic-based screening test (e.g., Pap test), regardless of HPV self-test return status. This will most likely apply to women in Group 2 health systems during the Usual Care Continued phase, but past studies have shown that some women will get a Pap test after receiving an HPV self-test in the mail (without using the self-test).⁴² All women not meeting one of these three criteria will be considered "unscreened." To determine this outcome, we will examine HPV self-test return status, HPV testing results, and EHR data (follow-up appointment attendance, Pap testing, etc.) for each sampled woman.

Among women who return their HPV self-test, we will examine the timing of device return and categorize each as returned within two weeks of distribution (i.e., prior to any PN) or after two weeks of distribution (i.e., following PN). We will also examine HPV testing results (positive or negative for high-risk HPV types) and collect data from EHR on the number of normal and abnormal clinic-based cervical cancer screening tests received by each woman and any cervical abnormalities found (i.e., low-grade squamous intraepithelial lesion, etc.).

To assess if the intervention is equitable (Figure 4), we will examine patient characteristics via data from HER (e.g., age and when their most recent clinic-based cervical cancer screening test prior to project entry occurred [if

ever]). Lastly, to assess safety, we will examine data from the patient satisfaction survey to see if women report any issues about using their HPV self-test. We do not anticipate such reports to be common, as HPV self-test devices have been used safely and easily by women in several research studies.⁶⁻¹⁵

Sample Size

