The project's total sample size will be 1800 women across Years 2-5 (900 women from Group 1 clinics/health systems and 900 from Group 2 clinics/health systems). These sample sizes are feasible given the expected sampling frame size (see Table 1) and will give us at least 90% power for the below analyses.⁴³ The power calculation assumed a two-sided alpha=0.05, an intraclass correlation coefficient<0.017 (based on our pilot study), and the below outcome occurrences.

Primary Analyses

Primary analyses will examine the proportion of women from Year 2 screened, as defined above, and use an intent-to-treat approach. To compare treatment groups (Group 1 vs. Group 2), we will use generalized linear mixed models (GLMMs) to account for the correlation between women from the same clinic,⁴⁴ though we expect cluster effects to be low (i.e., intraclass correlation coefficient<0.017 based on our pilot study). Since our outcome is binary, we will use a logit link to estimate odds ratios for the GLMMs. We expect that 30% of women from Group 1 clinics/health systems and 10% of women in Group 2 clinics/health systems will be categorized as screened. The primary model will be unadjusted, but we will conduct sensitivity analysis that include potential confounders due to imbalance from randomization ($p<0.10$ when comparing groups). Results will determine the effectiveness of the intervention in increasing cervical cancer screening compared to usual care.

Secondary Analyses

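### Covariates reach the treatment comparison only through an unnamed list and a p<0.10 baseline test in a sensitivity analysis; name them in advance instead

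*Combined protocol and SAP*

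**What the plan says.** All references are to the combined protocol and SAP, section 3.

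- **Randomization:** "Health system will be the unit of randomization", and "A 1:1 allocation scheme stratified by state will be used", giving five systems per group. Under Health Systems and Clinics: "The P01 program will involve a total of 10 health systems in four states". The number of systems in each state is not given.
- **Aim 1, Primary Analyses:** a logit GLMM of Year 2 screening, with clustering included "to account for the correlation between women from the same clinic". On covariates: "The primary model will be unadjusted, but we will conduct sensitivity analysis that include potential confounders due to imbalance from randomization". The criterion is p<0.10 when the groups are compared. No candidates are named and no level of testing is given.
- **Aim 1, Table 1 and Measures:** Table 1 lists "Demographic and health-related characteristics" under equitableness. Measures comes nearest to a candidate list, giving as examples of what will be taken from the EHR "age and when their most recent clinic-based cervical cancer screening test prior to project entry occurred", if there ever was one.
- **Aim 1, Secondary Analyses:** patient characteristics are fitted as predictors of being screened. They are the object of study there and do not adjust the treatment comparison.
- **State** is the stratification factor but is named in no model in the document.

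**The concern.** With five systems per arm, some chance imbalance in patient mix is to be expected, and the sensitivity analysis is the plan's only covariate-based check on it. As written, nobody can say beforehand what that analysis will contain.

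The selection rule has three weaknesses:

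- Under proper randomisation, a significance test of baseline differences tests a hypothesis already known to be true.
- It takes no account of whether a covariate predicts screening. A strong predictor with a modest imbalance is left out, and an irrelevant one with a large imbalance goes in.
- Its answer can change with the level at which the test is run, which is not stated. The same rule also cannot select state where randomisation has balanced it.

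At stake are the credibility of the sensitivity analysis and a little precision, since covariates already due to be collected are left out of the effectiveness model.

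**Working it through.** **Inputs from the plan.** 600 women per group in Year 2; five systems per group, so 600/5 = 120 per system on average; ICC below 0.017; 30% versus 10% screened; two-sided alpha 0.05; power stated as at least 90%.

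**Assumptions not in the plan.** Exactly 120 women in every system; a covariate ICC of 0.017 (range 0.005 to 0.05); one binary covariate with 40% prevalence and an odds ratio of 2 to 3 for screening.

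**1. The plan's power figure.** The design effect is 1 + 119 × 0.017 = 3.023, so the effective n is 600/3.023 = 198.5 per group. Power for 30% versus 10% is 99.9% by the normal approximation and 99.4% by non-central t on 8 df. The stated 90% is met.

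**2. How often the rule flags a covariate that differs only by chance.**
- On 5 versus 5 system means, t-test on 8 df: 10% by construction.
- On women ignoring clustering: 2 × [1 − Φ(1.645/√DEFF)].

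| Covariate ICC | DEFF | Flagged |
|---|---|---|
| 0.005 | 1.595 | 19% |
| 0.017 | 3.023 | 34% |
| 0.05 | 6.950 | 53% |

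**3. How often the system-level test misses an imbalance that has occurred.** Let σ be the true SD of the system means and s its estimate on 8 df. A realised arm difference d is flagged if d/(s√(2/5)) exceeds 1.860.
- d equal to one SD of the arm difference (σ√0.4): flagged if χ²₈ < 8/1.860² = 2.31, probability 3.0%. **Missed: 97%.**
- d equal to one SD of the system means (σ): flagged if χ²₈ < 8/(0.4 × 1.860²) = 5.78, probability 32.9%. **Missed: 67%.**

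**4. What a typical imbalance does to the result.** The SD of the arm difference in prevalence is √(2 × 0.24 × DEFF/600), which is 0.049 at covariate ICC 0.017 and 0.075 at 0.05. At a common 10% screening rate, the risk gap between women with and without the factor is 0.138 − 0.074 = 0.064 (OR 2) or 0.160 − 0.060 = 0.100 (OR 3). The shift is 0.049 × 0.064 = 0.3 points up to 0.075 × 0.100 = 0.75 points, against an expected 20.

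**5. What adjustment gains.** Within-arm variance explained is 0.24 × gap²/[p(1−p)]. At p = 0.10 this is 1.1% (OR 2) and 2.7% (OR 3). At p = 0.30, where the gaps are 0.147 and 0.232, it is 2.5% and 6.2%.

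**6. What adjustment does to the odds ratio.** The marginal value is (0.30/0.70)/(0.10/0.90) = 3.86. Integrating over a logit random effect with variance 0.057 to 0.108 (two readings of ICC 0.017) gives 3.90 to 3.94 in the planned cluster-conditional model. With the assumed factor added it is 4.00 to 4.04 (OR 2) or 4.15 to 4.20 (OR 3).

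**7. What state would cost in the primary model.** Four states use up to 3 of the 8 between-system df. The only layout of ten systems in four states that splits exactly 1:1 in every state is 4, 2, 2, 2, leaving 5 df. If state explains nothing, system-level power there falls from 99.4% to 98.1% at ICC 0.017, and from 95.4% to 91.2% at an assumed 0.03. The interval narrows only if state explains more than about 32% (ICC 0.017) or 27% (ICC 0.03) of between-system variance, a share that is not known.

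**The case against.** The strongest reply is that a prespecified unadjusted comparison of randomised groups is legitimate, so only the content of one sensitivity analysis is loose. The possible gain is slight: 1% to 6% of variance explained and a shift below one point, both resting on an assumed covariate. Nothing in the plan shows how strongly age or screening history predicts screening; the Secondary Analyses only set out to examine it. Most of this stands, and it is why the point is graded as an improvement. It does not rescue the p<0.10 rule, which still leaves that analysis undefined in advance.

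Timing is also a fair objection. The document is dated June 30, 2023, and the text for Year 4 introduces a new way of confirming eligibility. Whether Year 2 outcomes had been seen is not stated. If they had, replacing the primary model would itself be a post hoc choice, so the fix is made conditional on this.

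A reader might infer that leaving state out of the model invalidates or biases the primary test. The documents do not support that. Randomisation protects the unadjusted contrast, and in an analysis at system level, omitting a balanced stratification factor makes the test conservative. The level of clustering in the GLMM is a separate question and is not argued here.

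**Conclusion.** The point holds as a weakness of efficiency and prespecification. The primary model is unadjusted, the sensitivity covariates are not named, and the rule for choosing them ignores prognosis and depends on an unstated test level: about 10% versus 34% chance selection at covariate ICC 0.017. Run on systems, it would pass over about 97% of imbalances of one SD of the arm difference and about 67% of those of one SD of the system means.

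It is not a bias, and it does not threaten the stated power. At 30% versus 10% the primary conclusion is unlikely to change. The flag rate on women rests on equal system sizes and the assumed covariate ICC; the shift and precision figures rest also on the assumed prevalence and odds ratio. The miss rates need only roughly normal system means with equal variance. That the candidates are unnamed and the test level unstated rests on the text alone.

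**What to change.** 1. Delete the p<0.10 rule and describe baseline balance without tests.
2. Prespecify adjustment of the treatment comparison for woman-level age and time since last screening, with categories for never screened and for date missing.
3. If Year 2 outcomes have not been examined, make the adjusted GLMM primary and keep the unadjusted one as a sensitivity analysis. If they have, keep the unadjusted model primary, make the adjusted model the named sensitivity analysis, and label the change post hoc.
4. Optionally add one prespecified sensitivity model with state as a fixed effect and df counted on systems, pooling any single-system state before outcomes are seen. State need not enter the primary model.

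**Cost.** SAP text only. Both covariates are already planned from the EHR, and as woman-level terms they use no between-system df. There are three drawbacks. The odds ratio becomes conditional on the covariates as well as the cluster, about 4.0 to 4.2 instead of 3.9 under the assumed factor; a standardised risk difference beside it would help readers. The precision gain is small. Completeness of the last-test date is not stated, nor whether the EHR can separate never screened from missing, so this should be checked before the categories are fixed.

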Women in Group 2 clinics/health systems who did not get a clinic-based cervical cancer screening test in the 4-5 month period following the reminder letter being sent will be on a sampling frame to continue with usual care. We will randomly sample from this list, stratified by clinic. We will sample a total of 600 women across all Group 2 health systems. Similar to sampled women in Group 1, sampled women in Group 2 will first be sent a letter (see Appendix) asking them to confirm their eligibility criteria (as defined above). If women meet any criteria that would make them ineligible, they will be asked to indicate this information and return the letter in a provided postage-paid return envelope. Return of a letter will be considered consent for providing this information. Women who return their letter and are found to be ineligible will not continue in the project, and a potential replacement will be randomly sampled from the remaining list (who will then be sent a letter to confirm eligibility). Women who do not return a letter will be considered as confirmed eligible since only women who meet criteria making them ineligible will be asked to return their letter. The clinics will mail all of the reminder letters to women. Members of the project team will not have access to any identifying information (including contact information) of the patients. All communication between the project team and clinics about patients will involve only ID numbers.

Each woman who is confirmed eligible will next be mailed an additional reminder letter to get a clinic-based cervical cancer screening test (i.e., usual care continued; see Appendix) and an information sheet about cervical cancer (the same information sheet that will be sent to Group 1; see Appendix). These materials will be sent by the clinics,

as members of the project team will not have access to any identifying information (including contact information) of the patients. All communication between the project team and clinics about participants will involve only ID numbers.

Data Collection for Year 2

There will be two data collection activities at during Year 2: a medical record review and a patient satisfaction survey.

Medical Record Review

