The Bundling phase will occur in Group 1 clinics/health systems during Year 3. Implementation will mirror the Early Intervention phase, with the large difference being that all three projects in the P01 program will be occurring simultaneously during all of this project year (whereas the start of projects will be staggered during the Early Intervention phase).

In this phase, 100 eligible women across Group 1 health system who are unscreened/underscreened will be randomly sampled from the sampling frame and sent an HPV self-test. The methodology during the Bundling phase will mirror the methodology of the Active Intervention phase during Year 2.

Group 2: Delayed Intervention

Group 2 clinics/health systems will receive delayed intervention during Year 3. The methodology of this phase will be identical to the Group 1 Active Intervention during Year 2. In this phase, 100 eligible women across Group 2

health systems who are unscreened/underscreened will be randomly sampled from the sampling frame and sent a self-test.

Data Collection for Year 3

Similar to data collection during Year 2, data collection during Year 3 will include a medical record review and a patient satisfaction survey. As described for Year 2, members of the project team will not have access to any identifying information (including contact information) of the patients. All communication between the project team and clinics about participants will involve only ID numbers.

Medical Record Review

For all women in Groups 1 and 2, we will confirm whether women received a clinic-based cervical cancer screening test during Year 3. For women in Groups 1 and 2 who tested positive for a high-risk HPV type based on their self-test, we will confirm: a) any follow-up appointment attended; b) any follow-up care received; and c) any cervical abnormalities (precancerous and cancerous) found during this follow-up care.

Patient Satisfaction Survey

The survey and methodology will be identical to those described previously. We will send a survey to all women in Groups 1 and 2 who were sent an HPV self-test during Year 3.

Year 4 Randomized Trial Activities

Group 1: Sustainability

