We will conduct several secondary analyses for Aim 1. First, we will examine the proportion of HPV self-test returners who returned their self-test following receipt of PN. Results will provide valuable data on the added benefit of PN on HPV self-test return. Second, we will use GLMMs with a logit link to examine potential differences in the proportion of women screened across project years within each treatment group (i.e., comparing Years 2, 3, 4, and 5 for Group 1). Results will determine how screening rates changed over time, which will be key in assessing whether the intervention was maintained during the Bundling and Sustainability phases. Third, to assess if the intervention was equitable, we will use GLMMs with a logit link to examine if patient characteristics are associated with women being categorized as "screened". Fourth, to assess safety, we will descriptively examine women's reports of any issues experienced when using their HPV self-test. Lastly, we will descriptively examine the prevalence of high-risk HPV infection, abnormal clinic-based cervical cancer screening tests, and cervical abnormalities among women.

Aim 2 (Implementation Outcomes)

Implementation outcomes will examine the fidelity, sustainability, and cost-effectiveness of the intervention. We hypothesize that the intervention will be implemented with high fidelity and sustained by the clinics/health systems (Hypothesis 2a). We also hypothesize that the intervention will be a cost-effective strategy for increasing cervical cancer screening (Hypothesis 2b).

Fidelity

We will use several strategies to ensure and examine fidelity (i.e., the degree to which the intervention is conducted according to protocol). At the patient-level, we will develop an electronic tracking system to track all mailings (e.g., self-test distribution) and other data collection activities. At the provider level, we will conduct the provider education sessions using a standardized PowerPoint presentation. Data during the sessions will be collected using a checklist (for project team use only) that includes key observations related to fidelity (e.g. the presence of participants during entire session).

Sustainability

We will examine the screening rates during the Sustainability phase(s) for both Groups 1 and 2 to determine sustainability.

Cost-effectiveness

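### Maintenance is compared only across years within a group, where phase coincides with calendar year; Group 2 needs Year 3 as its reference, and same-year group contrasts should be added

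*Combined protocol and SAP*

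**What the plan says.** Under Aim 1, Secondary Analyses, logit mixed models will "examine potential differences in the proportion of women screened across project years within each treatment group". The years are listed for one group only ("i.e., comparing Years 2, 3, 4, and 5 for Group 1"), and no reference year is named for Group 2. The plan says of the result: "which will be key in assessing whether the intervention was maintained during the Bundling and Sustainability phases".

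Aim 2, Sustainability, adds one sentence: "We will examine the screening rates during the Sustainability phase(s) for both Groups 1 and 2 to determine sustainability". It gives no comparator, model or criterion. No between-group comparison after Year 2 is stated anywhere.

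On the schedule, Group 2 women in Year 2 "will be on a sampling frame to continue with usual care". Then "Group 2 clinics/health systems will receive delayed intervention during Year 3", and of that year the plan says: "The methodology of this phase will be identical to the Group 1 Active Intervention during Year 2". In the same Year 3, Group 1 is in Bundling, with "100 eligible women across Group 1 health system who are unscreened/underscreened" sampled.

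The eligibility procedure changes part-way. In Year 2 a woman who does not answer the eligibility letter counts as confirmed, and Year 3 follows the Year 2 methods. The Year 4 sections for both groups introduce a completed form that the woman has to return.

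**The concern.** If each phase sits in its own year or years, a within-group comparison of years cannot distinguish a phase effect from anything else that changed with the calendar, such as clinic access, background screening, or how women enter the sample. The Year 4 form is a concrete case. It starts exactly when Group 1 enters Sustainability and Group 2 enters Bundling. If only women who return it go on to receive a self-test, the later samples may respond better to mail, which could raise the screened proportion and hide a real loss.

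Group 2 has a second problem. Its series begins in a usual-care year, so a rise from Year 2 shows that the intervention arrived and says nothing about whether it was kept up.

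At stake is the reading of a secondary result that bears on the sustainability part of Hypothesis 2a.

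**Working it through.** **Inputs.** From the document: 600 women per group in Year 2 and 100 per group in each of Years 3, 4 and 5; five health systems per group; intraclass correlation below 0.017; expected screened proportions of 30% and 10% in Year 2. Assumed here: 30% in every intervention cell, different women sampled each year, and equal health-system sizes where clustering enters.

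**The plan's own figures.** Sample size: 2 × (600 + 3 × 100) = 1800, as stated. Year 2 power: 600/5 = 120 women per system; design effect 1 + 119 × 0.017 = 3.02; effective size 600/3.02 ≈ 198 per group; power for 30% against 10% is 99.9% (99.4% using t on 8 df). This agrees with the stated 90% or more. The only outcome rates given for that statement are those for Year 2.

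**Phase by year** (from the yearly sections and Table 3; Active means Early or Delayed Intervention):

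| | Year 2 | Year 3 | Year 4 | Year 5 |
|---|---|---|---|---|
| Group 1 | Active | Bundling | Sustainability | Sustainability |
| Group 2 | Usual care | Active | Bundling | Sustainability |
| Eligibility | silence counts | silence counts | form returned | form returned |

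The eligibility entry for Year 5 is read from the Year 4 wording, which introduces the form from that year onward.

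**Within a group.** There are four cells. An intercept and three year terms use all of them, so no phase term can be added (rank 4 for 7 columns in each group). If the form moves the screened proportion by Δ points in both groups, then:
- Group 1, Years 4-5 minus Year 2: Sustainability minus Active, plus Δ.
- Group 2, Year 4 minus Year 3: Bundling minus Active, plus Δ.
- Group 2, Year 5 minus Year 3: Sustainability minus Active, plus Δ.

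The document gives no value for Δ. A steady drift of 1, 3 or 5 points a year (assumed) would enter the Group 1 contrast multiplied by 2.5, the gap from Year 2 to the mean of Years 4 and 5, giving 2.5, 7.5 or 12.5 points.

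**Across groups in the same year.** Write D for Group 1 minus Group 2 in a given year, g for a constant group difference, and A, B, S for the phase effects. A year effect common to both groups cancels:
- D3 = g + B − A
- D4 = g + S − B
- D5 = g

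Hence B − A = D3 − D5, S − B = D4 − D5, and S − A = D3 + D4 − 2 × D5. A model with group, year and phase terms has 8 parameters for 8 group-year cells. It can be estimated, but it is saturated.

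**Precision before clustering**, with p(1 − p) = 0.21:

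| Contrast | Variance | SE (points) | 95% half-width |
|---|---|---|---|
| One D (100 vs 100) | 2 × 0.0021 = 0.0042 | 6.5 | 12.7 |
| B − A = D3 − D5 | 2 × 0.0042 = 0.0084 | 9.2 | 18.0 |
| S − A = D3 + D4 − 2 × D5 | 6 × 0.0042 = 0.0252 | 15.9 | 31.1 |
| Within Group 1, Year 2 vs Years 4-5 | 0.21/600 + 0.21/200 = 0.0014 | 3.7 | 7.3 |

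With clustering at 0.017 and a system effect constant over years, the adjusted SEs with a group term are 9.1 for B − A and 15.7 for S − A. Without a group term they are 7.2 and 11.2.

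**Power for a fall from 30% to 20%.** Within Group 1, 600 against 200, it is 80% ignoring clustering. For one same-year contrast, 100 against 100 with design effect 1 + 19 × 0.017 = 1.32, it is 29%.

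**Group 2 reference.** Suppose 10% in Year 2, 30% in Year 3 and 20% in Year 5 (the last is assumed). Against Year 2, Year 5 is +10 points. Against Year 3 it is −10, a loss of one third of the intervention-year rate.

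**The case against.** The best defence of the plan is precision. The within-Group 1 contrast has an SE of 3.7 points. Sustainability minus Active from the pooled model has 15.9, an interval of about ±31 points around an expected rate of 30%. Discarding the first for the second would exchange a possibly biased estimate for a nearly uninformative one. This stands, and it is why the within-group models should stay.

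A reader might infer that randomisation with staggered starts cleanly separates phase from year. It does so only if year and phase effects are additive and the same in both groups, and a saturated model cannot check that at the group-year level. There is reason for doubt. In Year 3, Group 1 systems have already had an intervention year with 600 women sampled, while Group 2 systems are in their first. Later samples come from women still unscreened, so depletion of the frame may differ by group. In Year 5 the phase is shared, but for Group 1 it is the second Sustainability year. No single same-year contrast compares Sustainability with Active Intervention.

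A reader might also infer that the Group 2 test is bound to reject under perfect maintenance. For 10% of 600 followed by three years at 30% of 100, the pooled proportion is 150/900 = 0.167. The 3-df noncentrality is then (600 × 0.0667² + 300 × 0.1333²)/0.1389 = 57.6, which gives power above 0.999. The arithmetic is sound, but the plan names no such omnibus test, and a model with year as a factor can supply Year 3 against Years 4 and 5. What remains is that the reference year is not stated.

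Finally, the plan does not let this one analysis decide Hypothesis 2a. That hypothesis also covers fidelity, and Aim 2 says only that rates will be examined.

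**Conclusion.** The concern holds as a gap in a secondary analysis. The only comparison stated for maintenance cannot separate phase from calendar year, and the protocol itself introduces a change in Year 4 that coincides with a change of phase in both groups. Any shift it causes enters the Group 1 Sustainability contrast in full. Its size and direction are unknown. Year 2 is not a valid maintenance reference for Group 2.

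Same-year contrasts remove whatever acts equally in both groups, at SEs of about 6.5 to 15.9 points before clustering. They are estimates, not powered tests. The figures assume 30% screened throughout and independent yearly samples. The phase-specific ones also need the additivity and common-effect assumptions above. The primary Year 2 comparison is not touched.

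**What to change.** In Aim 1, Secondary Analyses, with a cross-reference from Aim 2, Sustainability:

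- Keep the within-group models. For Group 2, name Year 3 (Delayed Intervention) as the maintenance reference and report Year 2 only as the usual-care level.
- Add the same-year between-group contrasts with intervals: Year 3, Bundling against Delayed Intervention; Year 4, Sustainability against Bundling; Year 5, both in Sustainability, as a check on the underlying group difference.
- Optionally, fit one logit mixed model to both groups with group, year and phase terms as a supportive analysis. State its assumptions: additive year and phase effects, the same in both groups, and no differential effect of time since start or of sampling-frame depletion.
- State the Year 4 change in eligibility confirmation as a limitation on within-group trends in both groups. Using Year 3 as the Group 2 reference does not remove it.
- Say that these contrasts are not powered.

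The cost is analysis-plan wording and some analysis time, with no new data. The drawback is wide intervals, which may leave the maintenance question open.
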